### Supportive analysis

The cumulative distribution of decline from baseline at 24 weeks and at 52 weeks in % predicted FVC will be graphically represented by treatment arm and by background therapy status without any imputation.

#### 2.4.4.1.1 Sensitivity analyses

The description of all sensitivity analyses is available on the below [Table 4](#):

**Table 4 - primary efficacy outcome algorithm in case of missing data**

Type of missing data	Sensitivity 1	Sensitivity 2
Missing data at week 52 due to reasons other than death or lung transplant	Multiple imputation of week 52 value using copy increment from reference (CIR) approach (assuming normality)	No imputation
Missing data at week 52 due to death	Multiple imputation of week 52 value using the distribution of the last available % Predicted FVC assessment of dead and lung transplanted patients	No imputation
Missing data at week 52 due to lung transplant	Multiple imputation of week 52 value using the distribution of the last available % Predicted FVC assessment of dead and lung transplanted patients	No imputation

**Sensitivity analysis 1:** Assessments at week 52 will be used regardless of whether the patient has previously discontinued treatment.

The absolute change from baseline to week 52 in %predicted FVC will be analyzed on the mITT population using a Mixed Model with Repeated Measures (MMRM) with the fixed categorical effects of treatment arm, stratification factor (with/without Background Therapy), time point, treatment-by-time point interaction, stratification factor-by-treatment-by-time point interaction, as well as the continuous fixed covariate of % predicted FVC baseline. Parameters will be estimated with the Newton-Raphson algorithm, an unstructured covariance matrix will model the within-patient errors, and the denominator degrees of freedom will be estimated using Satterthwaite's approximation.

As for primary analysis, the non-monotone missing patterns with a week 52 value available will not be imputed.

Week 52 missing values (due to reasons other than death or lung transplant) will be imputed using the CIR multiple imputation approach (3). The CIR approach is a multiple imputation methodology based on a Gaussian repeated-measures model:

- First, a large number of datasets will be imputed using the posterior distribution of a linear model containing:
  - baseline value,
  - week 12, week 24 and week 36 time points values (if occurred before the current time point to be imputed),
  - stratification factor,
  - treatment arm\* time point interaction,
  - treatment arm.

This requires a monotone missingness, which is why all time points will be imputed sequentially to determine week 52 value.

- Then, the analysis will be run independently on those imputed datasets to estimate parameters.
- Finally, all the results will be combined thanks to Rubin's rule.
- The particularity of this approach is that it will takes into account the disease progression:
  - Before withdrawal, all patterns have the same profile. A patient will be assumed to have the same mean response as his/her treatment arm.
  - After withdrawal (which results in missing values for all subsequent visits):
    - a patient in placebo arm will be imputed as in MAR framework.
    - a patient in active arm will be imputed assuming that the advantage due to past treatment is incremented with placebo slope assessed from withdrawal visit to imputed visit.

- In practice:
  - When running the imputation model, if the absolute change from baseline calculated from the predicted week 52 value is greater than zero (increases above baseline), it will be set to zero.
  - The MMRM will be performed on each imputed dataset.
  - The Rubin's rule will be performed using Roger's macro or MIANALYZE SAS procedure as appropriate
    - The number of datasets (1000 if appropriate) will be chosen to achieve p-value stability.

Week 52 missing data due to death or lung transplant will be imputed using the distribution of their last available % Predicted FVC assessment. The mean (SD) will be calculated and then, for each dead or lung transplanted patient, a value will be drawn several times (same number as for CIR methodology) between this mean and 0 (translation of this distribution with mean as maximal value achievable and right truncated at 0 if required). If the value drawn is higher than the last available patient's value, the imputed week 52 value will be set to the last available patient's value.

The SAR156597 qw arm will be tested versus Placebo at a type I error level of 5% first and if significant, will the SAR156597 q2w arm be tested versus Placebo at a two-sided type I error level of 5% using the appropriate contrast. The adjusted Least Square Means (LSMeans) estimates and standard errors (SE) will be provided for each of the 3 arms, adjusted differences of means (LSMEAN differences), corresponding standard errors (SE), 90% and 95% CIs will be assessed for each active arm versus placebo.

A specific table will describe the following items by treatment arm:

- The number (%) of patients with an observed week 52 value for % predicted FVC
  - The mean (SD) and median (Q1:Q3) of baseline and week 52 values of % predicted FVC for those patients
  - The mean (SD) and median (Q1:Q3) of absolute change from baseline at 52 weeks in % predicted FVC for those patients
- The number (%) of patients having a missing data due to death at week 52,
- The number (%) of patients having a missing data due to lung transplant at week 52,
- The number (%) of patients having a missing data due to reasons other than death or lung transplant,
- The mean (SD) of baseline % predicted FVC value for all patients included in the analysis,
- The LSMEANS (SE), the LSMEAN Differences versus placebo (SE, corresponding 90% and 95% CIs) and the p-values versus placebo of MMRM.

The representation of LSmeans (SE) over time will be displayed by treatment arm and background therapy status.

**Sensitivity analysis 2:** Only on-treatment data will be analyzed which means that only data during the treatment period (from randomization to last IMP administration date + 7 days) will be considered. Post-treatment data will be considered missing. Only patients having a baseline and a post-baseline (during the treatment period) % predicted FVC values in at least one time point analysis window will be considered in the analysis.

The absolute change from baseline to week 52 in %predicted FVC will be analyzed on the mITT population using a Mixed Model with Repeated Measures (MMRM) with the fixed categorical effects of treatment arm, stratification factor (with/without Background Therapy), time point, treatment-by-time point interaction, stratification factor-by-treatment-by-time point interaction, as well as the continuous fixed covariate of % predicted FVC baseline. Parameters will be estimated with the Newton-Raphson algorithm, an unstructured covariance matrix will model the within-patient errors, and the denominator degrees of freedom will be estimated using Satterthwaite's approximation.

No imputation of week 52 missing data due to death, lung transplant or reasons other than death or lung transplant will be performed.

The SAR156597 qw arm will be tested versus Placebo at a type I error level of 5% first and if significant, will the SAR156597 q2w arm be tested versus Placebo at a two-sided type I error level of 5% using the appropriate contrast. The adjusted Least Square Means (LSMeans) estimates and standard errors (SE) will be provided for each of the 3 arms, adjusted differences of means (LSMEAN differences), corresponding standard errors (SE), 90% and 95% CIs will be assessed for each active arm versus placebo.

A specific table will describe the following items by treatment arm:

- The number (%) of patients with an observed week 52 value for % predicted FVC
  - The mean (SD) and median (Q1:Q3) of baseline and week 52 values of % predicted FVC for those patients
  - The mean (SD) and median (Q1:Q3) of absolute change from baseline at 52 weeks in % predicted FVC for those patients
- The number (%) of patients having a missing data due to death at week 52,
- The number (%) of patients having a missing data due to lung transplant at week 52,
- The number (%) of patients having a missing data due to reasons other than death or lung transplant,
- The mean (SD) of baseline % predicted FVC value for all patients included in the analysis,
- The LSMEANS (SE), the LSMEAN differences versus placebo (SEs, corresponding 90% and 95% CIs) and the p-values versus placebo of MMRM.

The representation of LSmeans (SE) over time will be displayed by treatment arm and background therapy status.

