### **1.3 DETERMINATION OF SAMPLE SIZE**

Approximately 300 patients will be randomized in this study, 100 per treatment arm. Based on the enrollment in prior studies of this population approximately half of the patients are expected to be older than 65.

The sample size calculations are based on the primary efficacy variable of % predicted FVC change from baseline to week 52, with the following assumptions:

- A common standard deviation of 12% is assumed based on the data from previous trials (26)
- A 5% mean difference between each dose and placebo in change from baseline in % predicted FVC
- A 2-sided 5% significance level with 80% power

Ninety two (92) patients per treatment arm will yield 80% power to detect a 5 percentage point difference between the treatment groups and placebo. Additional patients will be randomized in each regimen to allow for dropouts; therefore, approximately 100 patients will be randomized into each treatment arm, for a total sample size of approximately 300 patients for the study.

[figure not shown]
As a rank-based method will be used for analysis the actual power may differ from these calculations, however, calculations based on the ASCEND study (28), which used the same analysis method and endpoint confirm that the planned analysis should have at least 80% power. No adjustment is made for multiplicity since a hierarchical testing procedure is proposed.

Calculations were made using nQuery Advisor 7.0.

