**Figure 1 - Graphical study design (screening period, double-blind period and follow-up period)**

R\*: randomization  
Sc: subcutaneous  
D: day  
W: week

Approximately 300 patients will be randomized in a ratio 1:1:1 to the following three treatment arms:

- SAR156597 (qw) arm (n = 100): Patients will receive SAR156597 administered subcutaneously in 200 mg doses once every week (qw)
- SAR156597 (q2w) arm (n = 100): Patients will receive SAR156597 administered subcutaneously in 200 mg doses once every 2 weeks (q2w) alternating with placebo subcutaneously once every 2 weeks
- Placebo (qw) arm (n = 100): Patients will receive placebo subcutaneously once every week.

The study population will be stratified at baseline according to a background therapy with pirfenidone or nintedanib (standard of care for IPF in authorized countries).

The study will last up to 68 weeks as follows:

- Up to 4 weeks of screening
- 52 weeks of study treatment (from Day 1 dosing to Week 52 dosing)
- 12 weeks of follow-up

The total duration will be approximately 64 weeks (excluding screening period) per patient.

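### Sensitivity analysis 1 caps multiply imputed week 52 changes at zero, so the imputed values are biased downward and no longer follow the stated copy-increment model; the effect is small

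*SAP*

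**What the plan says.** Sensitivity analysis 1 (SAP 2.4.4.1.1, Table 4 and the text below it) handles week 52 values missing for reasons other than death or transplant by CIR multiple imputation. First, "a large number of datasets will be imputed using the posterior distribution of a linear model" with baseline, earlier visits, stratum and treatment as terms. Placebo withdrawals are imputed under missing at random. Active withdrawals keep the advantage reached at withdrawal and then follow the placebo slope. An MMRM is fitted to each completed dataset and the results are pooled by Rubin's rule, with 1000 datasets suggested.

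Among the practical rules comes the cap: "When running the imputation model, if the absolute change from baseline calculated from the predicted week 52 value is greater than zero", the change is replaced by zero. Week 52 values that were observed are not altered, so an observed gain stays a gain. Weeks 12, 24 and 36 are imputed in sequence to reach week 52, but no cap is stated for them.

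The cap comes from the primary analysis. Protocol 11.4.2.1 applies it to a single regression prediction, and SAP 2.4.4.1 applies it to a single EBLUP per patient. The SAP gives no reason for extending it to multiple imputation and plans no version of Sensitivity analysis 1 without it.

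**The concern.** Capping one deterministic prediction limits an implausible extrapolation. Capping random draws does something else: multiple imputation is meant to represent the spread of plausible values, and with declines of the size expected here a sizeable share of valid draws lie above zero. Overwriting them lowers the mean of the imputed values and departs from the normal CIR model named in Table 4.

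The loss is larger where the imputed mean is nearer zero, so it differs between arms when a treatment effect exists. It also scales with the number of missing values in each arm, so it differs between arms when dropout is unequal.

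This matters because the primary rank test yields a p-value and descriptive tables, with no model-based difference or interval. Sensitivity analysis 2 gives LS-mean differences and intervals, but only for on-treatment data. Sensitivity analysis 1 is therefore the only LS-mean difference and confidence interval for the primary endpoint that uses data after treatment discontinuation. It also carries hierarchical 5% tests, and its model feeds the subgroup forest plot.

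**Working it through.** **The plan's own figure.** SAP 1.3 assumes 80% power, a two-sided 5% level, a 5-point difference and SD 12, and states: "Ninety two (92) patients per treatment arm will yield 80% power to detect a 5 percentage point difference between the treatment groups and placebo". The normal formula gives 2 × (1.960 + 0.842)² × 12² / 5² = 90.4, so 91. The t-test version gives 91.4, so 92, with power 0.803 at 92. The figure is reproduced. Since "approximately 100 patients will be randomized into each treatment arm", the implied dropout allowance is 8 in 100. No missing-data rate is stated.

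**Assumptions that are not in the documents.** Mean week 52 change on placebo of −6, −8 or −10; active 5 points better or equal; the 5 points accruing linearly over 52 weeks; dropout equally likely after weeks 12, 24 and 36; missing rates of 8 to 30%. Deaths and transplants are left out.

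**Step 1: effect of the cap on one set of draws.** For X ~ N(μ, σ), the share overwritten is Φ(μ/σ) and the mean falls by L(μ, σ) = μΦ(μ/σ) + σφ(μ/σ).
- μ = −5, σ = 12: L = −5 × 0.338 + 12 × 0.366 = 2.70. The mean becomes −7.7 and 34% are overwritten.
- μ = −5, σ = 8: L = −5 × 0.266 + 8 × 0.328 = 1.30. The mean becomes −6.3 and 27% are overwritten.
- μ = −10, σ = 12: L = 1.36, and 20% are overwritten.

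**Step 2: extra loss per imputed active patient under CIR.** The advantage kept is 5 × 12/52 = 1.15, 5 × 24/52 = 2.31 or 5 × 36/52 = 3.46 points. With placebo at −6, the active means are −4.85, −3.69 and −2.54.

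| σ | Mean active L | Placebo L | Extra loss |
|---|---|---|---|
| 6 | 1.01 | 0.50 | 0.51 |
| 8 | 1.70 | 1.05 | 0.65 |
| 12 | 3.18 | 2.37 | 0.81 |

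With placebo at −10, the extra loss is 0.33 (σ = 8) to 0.54 (σ = 12).

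**Step 3: effect on the treatment difference.** The shift is m_P × L_P − m_A × L_A, where m is the missing proportion in each arm. This was compared with a simulation: 100 per arm, four visits, SD 12 at week 52, sequential Bayesian CIR with 30 imputations, Rubin's rule and 1500 replicates. The week 52 difference in means stood in for the MMRM contrast. The closed form uses σ = 12.

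| Means P/A | Missing P/A | Uncapped | Capped | Simulated shift | Closed-form shift | Rubin SE |
|---|---|---|---|---|---|---|
| −10/−5 | 8/8% | 4.78 | 4.73 | −0.05 | −0.04 | 1.73 → 1.70 |
| −10/−5 | 20/20% | 4.47 | 4.36 | −0.11 | −0.11 | 1.77 → 1.69 |
| −10/−5 | 30/30% | 4.18 | 4.02 | −0.16 | −0.16 | 1.81 → 1.70 |
| −6/−1 | 20/20% | 4.47 | 4.32 | −0.14 | −0.16 | 1.77 → 1.67 |
| −6/−1 | 30/30% | 4.23 | 3.98 | −0.25 | −0.24 | 1.80 → 1.65 |
| −10/−5 | 30/10% | 4.65 | 4.88 | +0.22 | +0.22 | 1.78 → 1.70 |
| −8/−8 | 10/30% | 0.03 | −0.34 | −0.37 | −0.36 | 1.77 → 1.68 |

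The last row, for example, is (0.10 − 0.30) × L(−8, 12) = −0.20 × 1.81 = −0.36. The table uses a within-patient noise SD of 3; a noise SD of 7 changed every shift by about 0.01 or less.

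The uncapped estimates lie below 5 by design. CIR keeps on average 2.31 of the 5 points, so 8% missing gives 5 − 0.08 × 2.69 = 4.78.

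**Step 4: when the direction reverses.** The shift turns in favour of active when m_P/m_A exceeds L_A/L_P. With imputed means a full 5 points apart (−10 and −5), that ratio is 2.70/1.36 = 2.0 at σ = 12 and 1.30/0.405 = 3.2 at σ = 8. CIR keeps only part of the gap, so the ratio is lower: (1.36 + 0.54)/1.36 = 1.4 and (0.405 + 0.33)/0.405 = 1.8. A placebo missing rate 2 to 3 times the active rate is therefore enough.

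**Step 5: the standard error.** Across 16 settings (eight scenarios, two noise levels) the cap cut the between-imputation variance by about 30 to 46% and Rubin's SE by about 2 to 10%. Rubin's SE divided by the empirical SD was 1.05 to 1.21 uncapped and 1.03 to 1.15 capped, with Monte Carlo error about 2%. With no effect and 30% missing in each arm (noise SD 3), rejection was 2.4% uncapped and 3.0% capped.

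**The case against.** - **It is negligible at the planned missingness.** This stands. At 8% the shift is 0.05 points, about 1% of the design difference. Patients who stop treatment stay in follow-up with FVC (Protocol 4.2.1 and 10.3.4), and the week 52 window runs from day 309 to day 406 (SAP Table 6). Both limit missing values.
- **It is only a sensitivity analysis, and the cap keeps it aligned with the primary rule.** The first part stands. The second explains the rule but does not justify it, because a cap on draws is a different operation from a cap on one prediction.
- **The wording is open.** The term predicted in "When running the imputation model, if the absolute change from baseline calculated from the predicted week 52 value is greater than zero" is also used in SAP 2.4.4.1 for the deterministic EBLUP. If it meant the conditional mean before noise is added, the bias would be smaller; that case was not calculated. The draw is the more natural reading, since each imputed dataset contains draws.
- **SD 12 is a planning SD for all patients, and imputation conditions on earlier visits.** This bears on any single patient's draws. It does not shrink the average shift much: the simulated shifts hardly changed between the two noise levels and match the closed form at SD 12.
- **A reader might infer that the standard error is too small.** The documents and the check do not support this. The cap narrows the imputation spread but also the real sampling spread, and Rubin's rule is already conservative under CIR.
- **A reader might infer a loss of 1.4 to 1.9 points more per imputed active patient.** That places active withdrawals at −1 and placebo at −6 at week 52. Under the SAP's CIR rule they keep only the advantage reached at withdrawal, which gives 0.5 to 0.8.

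**Conclusion.** Wrong as written, minor in size. On the natural reading, the rule replaces valid random draws by zero. The imputed week 52 values then do not follow the stated Gaussian CIR model and are biased downward, while observed gains are untouched.

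With similar missingness the estimated effect moves toward zero, by about 0.05 points at 8% missing and 0.1 to 0.25 at 20 to 30%. It would be tempting to call the cap simply conservative, or to say that it always costs the better arm more. That does not hold for the contrast. With 30% missing on placebo and 10% on active it moved the estimate by +0.22 in favour of active, and rejection rose from 75.9% to 83.5%. With no true effect and 10% against 30% missing it produced −0.37. A missing-data sensitivity analysis should not have its direction set by the dropout pattern in this way.

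Rubin's SE is reduced, but not shown to be too small. All sizes rest on the assumed means, missing rates and dropout timing listed above. Only SD 12, the 5-point difference and the 92 and 100 per arm come from the plan.

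**What to change.** Delete the zero-cap bullet from Sensitivity analysis 1 and state instead: *week 52 draws from the CIR model are used as drawn, with no upper limit on the imputed change*. If alignment with the primary analysis is wanted, keep the capped version only as an additional analysis and report both. Do not move the cap to the conditional mean before noise is added: that is not CIR either. The primary analysis rule and the separate handling of deaths and transplants are not affected.

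The cost is one bullet, with no effect on design or data collection. The downside is that Sensitivity analysis 1 no longer shares the primary analysis's zero-cap rule and may be slightly less conservative.

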#### 2.4.4.1.2 Subgroups analyses

The following subgroups will be explored:

- Smoking status: Smoke / Never Smoke
- Gender: Male / Female
- Age: Age  $\leq 65$  / Age  $> 65$
- Stratification factor: With / Without background therapy
- % predicted FVC categories at baseline (using terciles: ( $\leq 60$ ,  $> 60$  and  $\leq 75$ ,  $> 75$ ))
- ANA at baseline: Positive / Negative where a Positive ANA titer is defined as titer  $\geq 1:40$

For each subgroup, the change from baseline at 52 weeks in % Predicted FVC will be analyzed using a rank ANCOVA model. For each pool of active arm vs placebo (A and B), the subgroup-by-treatment interaction will be tested as follows:

A) For Smoking status, Gender, Age subgroups: rank ANCOVA model with covariate baseline and terms of treatment, stratification factor, subgroup, treatment-by-subgroup

i. First, compute ranks of baseline and response as in the primary analysis

```
proc rank data=xxx nplus1 ties=mean out=rankdata;  
by stratum;  
var base ranks;  
ranks base_Rank ranks_Rank;  
run;
```

ii. Then, calculate the residuals as in the primary analysis

```
proc glm data=xx;  
by stratum;  
model ranks_Rank=base_Rank;  
output out=residual r=resid;  
run;
```

iii. Finally, the subgroup-by-treatment interaction will be tested using residuals with PROC GLM

```
proc glm data=residual;  
class armn subgroup stratum;  
model resid=stratum armn subgroup subgroup*armn;  
run;
```

B) For Stratification factor subgroup: rank ANCOVA model with covariate baseline and terms of treatment, stratification factor, treatment-by-stratification factor

- i. First, compute ranks of baseline and response without by stratum statement

```
proc rank data=xxx nplus1 ties=mean out=rankdata;  
var base ranks;  
ranks base_Rank ranks_Rank;  
run;
```

- ii. Then, calculate the residuals without by stratum statement

```
proc glm data=xx;  
model ranks_Rank=base_Rank;  
output out=residual r=resid;  
run;
```

- iii. Finally, the subgroup-by-treatment interaction will be tested using residuals with PROC GLM

```
proc glm data=residual;  
class armn stratum;  
model resid=stratum armn stratum*armn;  
run;
```

C) For % predicted FVC baseline categories: rank ANCOVA model with terms of treatment, stratification factor, subgroup, treatment-by-subgroup

- i. First, compute ranks of response as in the primary analysis

```
proc rank data=xxx nplus1 ties=mean out=rankdata;  
by stratum;  
var ranks;  
ranks ranks_Rank;  
run;
```

- ii. Second, the subgroup-by-treatment interaction will be tested using response ranks with PROC GLM

```
proc glm data=residual;  
class armn subgroup stratum;  
model ranks_Rank=stratum armn subgroup subgroup*armn;  
run;
```

Descriptive statistics of baseline values, week 52 values and change from baseline at 52 weeks in %predicted FVC including number (%) of patients, mean, SD, median, Q1, Q3, Min, Max by subgroup will be reported by treatment arm without any imputation.

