**Table 1 - Protocol amendment statistical changes**

Amendment Number	Date Approved	Rationale	Description of statistical changes
10	21-Jul-2015	An early analysis of the main efficacy endpoints and safety data will be performed after the last patient completed the End of treatment visit (Visit 9, week 52) to allow an evaluation of the benefit/risk for the treatment of IPF with SAR156597 and take the decision to move to Phase 3 of clinical development and prepare for future phase 3 studies.	Not applicable.
10	21-Jul-2015	In case of major recruitment issues, a futility analysis could be considered in order to make further decisions regarding trial continuation/discontinuation.	No major recruitment issues occurred during the enrollment therefore no interim analysis was performed.
10	21-Jul-2015	Due to the recent approval of pirfenidone (Esbriet®) and nintedanib (Ofev®) and thus the availability on the market in almost all countries participating in the study, the rate of patients with authorized background therapy is likely to be higher than that initially expected at time of study design. In consequence, in order to limit the impact of background therapy on efficacy and safety assessment of SAR156597 for the treatment of IPF, the rate of patients in the background therapy stratum will be capped to a maximum of 66% (i.e., 33% in the without background therapy stratum).	In protocol: stratification factor was already planned for primary analysis but was not described for secondary analyses.  In SAP, description for secondary analyses and specification whether specific parameters will be described by With/Without Background Therapy status will be specified.
NA	NA	Duration of IMP exposure is defined as: last dose date – first dose date + 14 days, however for 200 mg SAR156597 q2w arm, there is an IMP injection every two weeks alternating with placebo the other week.	Duration of IMP exposure will be defined as: last dose date – first dose date + 7 days.
NA	NA	Change in mITT definition due a too low selection of patients (more than 5% of patients were discarded with the protocol definition).	The new definition is all randomized patients who take at least one dose or part of a dose of IMP. Patients will be analyzed using the treatment arm to which they were randomized. This results in considering all mITT patients

Amendment Number	Date Approved	Rationale	Description of statistical changes

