- ii. Other patients (patients in active arm and not taking treatment at 52 weeks; or patients in placebo arm): Missing values at 52 weeks will be imputed using a model estimated from the subset of patients in the placebo arm who completed the 52-week treatment period and with a week 52 value. The imputation model will be based on a Mixed Model with Repeated Measures (MMRM) with fixed categorical effect of stratification factor (with/without Background Therapy) and repeated categorical effect for time point (baseline, week 12, week 24, week 36, week 52). Parameters will be estimated with the Newton-Raphson algorithm, an unstructured covariance matrix will model the within-patient errors, and the denominator degrees of freedom will be estimated using

- Satterthwaite's approximation. Missing values at 52 weeks will be imputed using the empirical best linear unbiased prediction (EBLUP).
- iii. When running the imputation model, if the predicted absolute change from baseline calculated from the predicted week 52 value is greater than zero (increases above baseline), it will be set to zero.
  - iv. The non-monotone missing patterns with a week 52 value available will not be imputed.
- b) Week 52 missing values due to lung transplant:
    - i. Any % predicted FVC value assessed after a lung transplant will be considered as missing.
    - ii. No imputation of a week 52 value for % predicted FVC. In step 2, patients will be ranked worse than missing data due to reasons other than death or lung transplant.
  - c) Week 52 missing values due to death :
    - i. No imputation of a week 52 value for % predicted FVC. In step 2, patients will be ranked worse than missing data due to lung transplant.
2. Rank ANCOVA
- a) Ranking within each stratum of the stratification factor (with/without Background Therapy)
    - i. Death: Missing data due to death will be ranked based on a time-to-death, with shortest time until death as the worst (lowest) rank (from 1 to  $n_{\text{stratum,death}}$ ).
    - ii. Lung transplant: Missing data due to lung transplant will be ranked based on a time-to-lung transplant, with shortest time until lung transplant as the worst (lowest) rank (from  $n_{\text{stratum,death}}+1$  to  $n_{\text{stratum,death}}+n_{\text{stratum,lungtransplant}}$ ). So, missing data due to lung transplant will be less penalized than deaths.

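### The rank-based test of treatment by background therapy re-ranks within-stratum ranks across strata, so with strata of unequal size this exploratory p-value does not test equal treatment effects

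*SAP*

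**What the plan says.** In the primary analysis (SAP 2.4.4.1), step 2a is headed "Ranking within each stratum of the stratification factor (with/without Background Therapy". Within a stratum, deaths take the lowest ranks by time to death. Transplants follow by time to transplant, then the observed or imputed FVC changes, up to the stratum size. Only then does PROC RANK with NPLUS1, by stratum, standardize those ranks.

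The subgroup section (SAP 2.4.4.1.2) gives code for three cases:

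- Part A (smoking, gender, age) begins "First, compute ranks of baseline and response as in the primary analysis" and runs PROC RANK by stratum on `base` and `ranks`.
- Part B (the stratification factor) begins "First, compute ranks of baseline and response without by stratum statement". It passes the same two variables with the BY line removed, takes residuals over the whole pool, and tests `stratum*armn`.
- Part C (baseline FVC categories) uses `ranks` again, by stratum.

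No step in the SAP orders the response over both strata. On stratum size, SAP Table 1 says "the rate of patients in the background therapy stratum will be capped to a maximum of 66" per cent and puts the other stratum at 33%.

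**The concern.** Part B should ask whether the drug effect on Week 52 change in % predicted FVC is the same with and without background therapy. That needs a response scale common to both strata. Baseline gets one, because `base` is the raw value and is ranked over the pool. The response does not: integers running from 1 to the size of the larger stratum are mixed with integers running from 1 to the size of the smaller. The best patient in the smaller stratum then ties with a mid-ranked patient in the larger one, and a given FVC benefit moves ranks less in the smaller stratum.

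Background therapy is the trial's only stratification factor. SAP Table 1 gives limiting its impact on the efficacy and safety assessment as the reason for the cap, and says the Week 52 analysis will inform the move to Phase 3. A misleading interaction p-value here could colour how the drug is thought to work on top of standard care.

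**Working it through.** **Inputs.** From SAP 1.3: SD 12 points, design difference 5 points, 100 patients per arm, so 200 in one active-plus-placebo pool. From SAP 1.1 and Table 1: at most 66% with background therapy, so 0.66 × 200 = 132 with and 68 without if the cap is reached. Assumed: 6% deaths unrelated to arm, and a two-sided 5% level, because the SAP sets no level for interaction tests.

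**The plan's own figure.** The documents give no figure for this interaction test. For the main comparison, 2 × (1.960 + 0.842)² × 12² / 5² = 90.4, so 91 by the normal approximation. The exact t-test gives power 0.798 at 91 and 0.803 at 92 per arm. This reproduces the plan's statement: "Ninety two (92) patients per treatment arm will yield 80% power to detect a 5 percentage point difference".

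**What the code does to the scale at 132/68.**

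- A within-stratum rank r up to 68 occurs once in each stratum, so its mean tied rank in the pool is 2r − 0.5. A rank above 68 occurs only in the larger stratum and becomes r + 68. Both are divided by 201.
- The top of the smaller stratum is (2 × 68 − 0.5)/201 = 0.67. The top of the larger is 200/201 = 0.995.
- On the within-stratum scale u = r/69, the smaller stratum has slope 2 × 69/201 = 0.69. In the larger stratum (u = r/133) the slope is 2 × 133/201 = 1.32 for the lower 68 patients and 133/201 = 0.66 for the upper 64, averaging (68 × 1.32 + 64 × 0.66)/132 = 1.00.
- The smaller stratum's effect should therefore shrink to roughly 0.69.

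Simulation agrees. With equal 5-point benefits and 6% deaths, the rank effects are 0.098 (with) and 0.069 (without), a ratio of 0.70. A single ranking over the pool gives 0.101 and 0.102. Without deaths the coded ratio is 0.078/0.116 = 0.67, and benefits of 5 and 7.5 points look equal (0.115 and 0.113).

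**Rejection rate of `stratum*armn`, 132/68, 6% deaths.** Change has a slope of 0.1 on baseline. There are 6,000 replicates per row, or 3,000 in rows marked *. The Monte Carlo standard error is at most √(0.25/3000) = 0.9 percentage points.

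| Benefit with / without background therapy (points) | As coded | Response ranked once over the pool |
|---|---|---|
| 0 / 0 | 2.8% | 4.7% |
| 5 / 5 | 4.5% | 5.3% |
| 10 / 10* | 9.5% | 5.0% |
| 5 / 10 | 4.3% | 21.1% |
| 2.5 / 10 | 14.2% | 41.5% |
| 0 / 10 | 36.9% | 64.4% |
| 10 / 5* | 35% | 23% |
| 10 / 0 | 71.5% | 65.4% |

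Repeat runs of the 5/10 row gave 3% to 4% against 21% to 22%.

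**Dependence on the split.** Benefits 5/10, no deaths, 4,000 runs:

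| Patients with / without | As coded | Ranked once |
|---|---|---|
| 132 / 68 | 3.5% | 26.4% |
| 120 / 80 | 8.8% | 28.4% |
| 100 / 100 | 27.2% | 30.5% |
| 80 / 120 | 43.7% | 29.1% |

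The distortion follows the imbalance: it nearly vanishes at equal sizes and reverses when the stratum without background therapy is the larger.

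**The case against.** The strongest reply is that the prose of part B already asks for the right thing: ranks of the response, without stratum. The code is schematic, with placeholder dataset names, and the SAP never formally defines `ranks`. A programmer who first built a pooled ordering would get a valid test. That is fair as to intent. But the same name serves parts A, B and C, part A ties it to the primary analysis, and the only response ordering the SAP describes is within stratum. Followed literally, the code gives the distorted test.

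Second, the plan has another route to the question. The supportive analysis after SAP 2.4.4.1.2 tests subgroup by treatment by time point with the MMRM of Sensitivity analysis 1. It covers the stratification factor explicitly, works on the FVC scale, and adds a forest plot with 95% confidence intervals. SAP 2.4.4.1 also tabulates results by background therapy status. This stands. A reader might infer that the trial would be blind to a difference between strata; the documents do not support that. The MMRM does not repair the rank-based p-value, however, and it handles deaths differently, by imputing FVC values.

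Third, power for a design-size difference is low even when the test is right: for 0 versus 5 points with 6% deaths, about 21%, against 10% as coded. A non-significant result would say little either way. This limits the consequence but does not justify the wrong scale.

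**Conclusion.** Part B is wrong as written. The damage is confined to one exploratory interaction p-value in each of the two pools (qw and q2w versus placebo). Under the stated assumptions, a larger benefit in the smaller stratum is under-detected, a larger benefit in the bigger stratum is over-detected, and large equal benefits of 10 points give about 10% false rejections.

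The documents do not support four stronger readings:

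- **That the primary test is compromised.** It ranks, adjusts and tests by stratum, so the fault does not reach it. The interaction tests also lie outside the hierarchy in SAP 2.4.4.3.
- **That effects scale in proportion to stratum size.** That would give 68/132 = 0.52. The actual factor is about 0.7.
- **That the p-value misleads in every case.** Equal benefits at the design size of 5 points do not inflate rejection, and with no effect the test is conservative (2.8%).
- **That patients without background therapy necessarily lose out.** The 66% is a maximum, and the direction depends on which stratum turns out smaller. Table 1 does expect background use to be higher than first planned.

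The conclusion rests on reading `ranks` as the step 2a within-stratum ranks. The sizes rest on the assumed split, death rate and 5% level.

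**What to change.** In SAP 2.4.4.1.2 part B, state that the step 2a ordering is rebuilt once across both strata of the pool: deaths by time to death, then transplants by time to transplant, then observed or imputed change in % predicted FVC. Use that ordering, not the within-stratum `ranks`, as the response input to PROC RANK without the BY statement. The residual and PROC GLM steps can stay as written.

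The cost is one sentence of SAP text and one derivation step before the existing code. It needs no new data and no change to trial conduct.
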